3.5 Safety Analyses

All safety analyses will be based on the Safety Population. Safety analyses in general will be descriptive and will be presented by treatment group in tabular format. Categorical endpoints will be summarized using the number and percentage of participants within each category. Continuous endpoints will be summarized descriptively with summary statistics (number, mean, standard deviation, standard error, median, first quartile, third quartile, minimum, and maximum).

3.5.1 Adverse Events (AEs)

All AEs will be coded to system organ class and preferred term using MedDRA. Treatment emergent adverse events (TEAEs) are defined as AEs with onset after the start of study treatment (PSL or placebo) through the end of study. Adverse events of special interest (AESI) include , acute graft versus host disease (GVHD), chronic GVHD, graft failure and rejection, cytokine release syndrome (CRS), and infusion-related AEs. These AESI will be reviewed by the DSMB as per the DSMB Charter.

An overall summary of AEs will be produced by treatment group. The numbers and percentages of participants will be provided for the following:

- Any TEAEs
- Any TEAEs by severity
- Any treatment-related TEAEs

- Any treatment-emergent AESIs (TEAESIs)
- Any treatment-related TEAESIs
- Any treatment-emergent serious AEs (TESAEs)
- Any treatment-related TESAEs
- Any TEAEs leading to discontinuation of study treatment
- Any TEAEs leading to discontinuation of study
- Any TEAEs leading to death

All the TEAE categories will be summarized by system organ class (SOC) and preferred term (PT). Participants with multiple AEs will be counted only once per SOC and PT. In addition, the TEAEs will be summarized by PT only. The number and percentage of participants with TEAEs, TESAEs and TEAESIs will be tabulated by PT and by the highest CTCAE Grade. CRS will only be graded by ASTCT grade.

Listings will be presented specifically for any AEs, deaths, SAEs, AESI, and TEAEs leading to discontinuation of study treatment and study.

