8.1.4 Adverse Events of Special Interest

The Investigator will monitor each participant for clinical and laboratory evidence for pre-defined AESI throughout participation in this study.

The Investigator will assess and record any additional information on the AESI in detail on an adverse event form, which must be submitted within 24 hours of awareness of the event.

For this study, AESI include the following:

- Acute and chronic GVHD (new onset or worsening of existing GVHD) (for the acute and chronic GVHD grading scales, see Appendix E).
- Graft failure and rejection.
- CRS (for the CRS grading scale, see Appendix F).
- Infusion-related adverse events.

During the study, additional AESI may be identified by the Sponsor.

Adverse events of special interest must be recorded in the eCRF.

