9.2.2 Analysis of Safety

The safety profile will be based on treatment-emergent adverse events (TEAEs) and changes in vital signs, physical examinations, clinical laboratory assessments, and ECGs. All safety analyses will be based on the Safety Population.

Safety analyses in general will be descriptive and will be presented by phase and treatment group in tabular format. Categorical endpoints will be summarized using the number and percentage of participants within each category. Continuous endpoints will be summarized descriptively with summary statistics (number, mean, standard deviation, standard error, median, first quartile, third quartile, minimum, and maximum).

A TEAE is defined as an adverse event with onset after the start of study treatment (PSL or placebo). The number and percentage of participants with TEAEs will be tabulated by MedDRA System Organ Class and Preferred Term for each treatment group and by severity and relationship to treatment. Adverse events leading to discontinuation of the study and SAEs will be summarized by treatment group. By-participant listings will also be provided for any deaths, SAEs, and adverse events leading to discontinuation of the study.

The key safety endpoint for this study is the incidence and severity of acute GVHD. The incidence and severity of acute GVHD, chronic GVHD, and CRS, and the corresponding exact binomial confidence intervals with 95% confidence level will be presented by treatment group.

Descriptive statistics will be provided for clinical laboratory data, vital sign data, and ECG parameters, presented as both actual values and changes from baseline over time. Abnormal physical examination findings will be presented in a by-participant data listing.

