3.1.7 Handling of Missing Data

In general, data will be analyzed and presented as observed and will not be imputed for the analysis of efficacy and safety.

In case the start and end dates for adverse events (AEs) and concomitant medications/procedures are missing or incomplete, the missing component(s) will be assumed as the most conservative value possible. For example, AEs with missing start dates, but with stop dates either overlapping into the treatment period or missing, will be counted as treatment-emergent, taking the worst-case approach. When partial dates are present in the data, both a partial start date and/or a partial stop date will be evaluated to determine whether it can be conclusively established that the AE started prior to the start of study treatment or ended prior to the start of study treatment. If the above cannot be conclusively established based on the partial and/or present dates, then the AE will be considered as treatment emergent. Actual data values as they appear in the original case report forms (CRFs) will be presented in the data listings.

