3.5.2 AEs of Special Interest

The AESIs will be reviewed by the DSMB as per the DSMB Charter. Criteria for acute and chronic GVHD and CRS can be found in Protocol Appendices E, F and G. The number and percentage of participants who had the treatment-emergent AESIs will be summarized by treatment group:

- Severity and incidence of acute GVHD
- Severity and incidence of chronic GVHD
- Severity and incidence of CRS
- Severity and incidence of infusion-related AEs
- Severity and incidence of graft failure and rejection

For GVHD, a separate table will be prepared that summarizes:

- aGVHD by MAGIC overall grade and by stage and organ involvement
- cGVHD by NIH score

Subgroup analyses may be conducted for the severity and incidence of acute GVHD by HLA Class (I, II, and I & II) and the number of HLA matches.

Incidence and severity of AESI and the corresponding exact binomial confidence intervals with 95% confidence level will be presented by treatment group.

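### The treatment-emergent flag tests onset only, so GVHD that starts before the first infusion and worsens after it can be missing from the by-arm AESI tables

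*SAP*

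**What the plan says.** Both documents define a treatment-emergent adverse event (TEAE) by onset. SAP 3.5.1 has "AEs with onset after the start of study treatment (PSL or placebo) through the end of study". Protocol 9.2.2 has "A TEAE is defined as an adverse event with onset after the start of study treatment (PSL or placebo". Neither adds a clause for worsening.

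The GVHD event of special interest is defined more broadly. Protocol 8.1.4 lists "Acute and chronic GVHD (new onset or worsening of existing GVHD".

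The SAP puts the onset-based flag on that event. In SAP 3.5.2, "The number and percentage of participants who had the treatment-emergent AESIs will be summarized by treatment group", and acute and chronic GVHD are both in the list that follows. Later in the same section, "Incidence and severity of AESI and the corresponding exact binomial confidence intervals with 95% confidence level will be presented by treatment group". That sentence does not repeat the treatment-emergent restriction.

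On importance, Protocol 9.2.2 says: "The key safety endpoint for this study is the incidence and severity of acute GVHD".

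On recording, Protocol 8.1 collects adverse events from informed consent onwards. A condition already present at consent goes into medical history and becomes an adverse event only if it gets worse. Clinically significant laboratory or examination findings present at randomization are also reportable if they worsen significantly.

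**The concern.** The event definition and the table filter do not match. The protocol counts a worsening of existing GVHD as an event, but the filter on the by-arm tables asks only when the adverse event began. Collection starts at consent, before any infusion, so a GVHD adverse event can carry a pre-infusion onset date. If it then worsens after the cells are given, neither document says that the worsening needs a new record or a new date. Whether the participant is counted can therefore depend on how the site keeps its adverse event record.

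What is at stake is the by-arm count for the key safety endpoint of a T cell product whose main theoretical risk is GVHD. The protocol treats worsening as clinically decisive elsewhere: under Protocol 3.1 and 6.5.1, GVHD that is worse than at randomization bars the second infusion. Yet no planned table is stated to compare post-infusion GVHD grade with pre-infusion grade.

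**Working it through.** The plan gives no figure to reproduce, and no alpha, power or effect size is involved. The check sets the recording rules (Protocol 8.1 and 8.1.4) against the flag (SAP 3.5.1, Protocol 9.2.2) for each way in which GVHD can arise. SAP 3.1.2 notes that the protocol puts randomization and first dose on the same day, so the interval between consent and first infusion is in effect the screening period.

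| Case | How it is recorded | Treatment-emergent under the current rule? |
|---|---|---|
| 1. GVHD first appears after the first infusion | New adverse event | Yes |
| 2. GVHD present at consent, worsens after infusion | Medical history; the worsening creates the adverse event | Yes, if dated at the worsening, which is the natural reading |
| 3a. GVHD first appears between consent and infusion, worsens after infusion, site opens a new record | Second adverse event dated at the worsening | Yes |
| 3b. As 3a, but the site keeps one record and raises its grade | One adverse event with its pre-infusion onset date | No, although the worsening meets the AESI definition |

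Only case 3b is lost.

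**Does the date-handling rule rescue case 3b?** SAP 3.1.7 covers missing and partial dates. With a missing start date, "AEs with missing start dates, but with stop dates either overlapping into the treatment period or missing, will be counted as treatment-emergent". With a partial date, the test is whether "it can be conclusively established that the AE started prior to the start of study treatment". A record with a complete pre-infusion onset date falls under neither provision, so SAP 3.5.1 alone decides, and it gives no.

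**Where does a case 3b event still appear?**
- In the adverse event and AESI listings (SAP 3.5.1), which are not limited to treatment-emergent events.
- In the DSMB's AESI summaries, supplied at least monthly (Protocol 3.2).
- Possibly in the MAGIC grade table and the exact-interval summary (SAP 3.5.2, Protocol 9.2.2). Neither is stated to be limited to treatment-emergent events, so the numerator of the exact interval is left open.

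**Are the data for a comparison with pre-infusion grade already scheduled?** The acute GVHD row of Protocol Appendix A has 8 marks. Read by column order, because the column headings did not survive in the public text, 2 precede the first infusion (screening, Day 0) and 6 follow it (Weeks 1, 2, 4, 6, 12 and 24): 2 + 6 = 8. A shift table therefore needs no new GVHD assessment.

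**The case against.** The strongest reply is that existing rules already capture nearly everything. GVHD present at consent becomes an adverse event by worsening. Significant worsening of findings present at randomization is reportable. Protocol 8.1.4 makes the worsening of GVHD an event in itself, to be submitted on an adverse event form within 24 hours of awareness. If the worsening is the reportable event, its natural onset date is the date of worsening. What remains is a data-entry convention, and the eCRF completion instructions, which might settle it, are not among the documents. It can also be said that the AESI definition describes a type of event and the TEAE definition a timing, so they need not be worded alike, and that the SAP follows the protocol's own TEAE definition.

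Much of this stands. It confines the gap to case 3b, and it means that both documents need the change. It does not close the gap: the flag depends on a date that no section fixes, and listings do not replace by-arm incidence.

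Three stronger inferences are tempting but not supported:
- **That the gap matters more because acute GVHD up to Grade 2 is allowed at entry (Protocol 4.2).** GVHD present at consent follows case 2 and is not lost. The entry criterion says little about how often GVHD first appears during screening.
- **That SAP 3.1.7 is itself defective because it counts an undated event but not a dated one that worsens.** It is an ordinary conservative rule for missing and partial dates and does not address complete dates.
- **That the lost events favour posoleucel.** The rule is the same in both arms and recording is blinded, so no direction is shown.

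**Conclusion.** The point holds in a narrow form and is minor. As written, the rule leaves a post-infusion worsening of GVHD out of the treatment-emergent AESI tables when the event began between consent and first infusion and the site kept the one record. This is a stated rule that miscounts that case, not merely missing detail.

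The number of participants affected cannot be derived. It would need the rate of new GVHD during screening, the share that worsens after infusion, and the share of sites that keep one record, and the documents give none of these. It is probably small. A reader should not infer that GVHD signals would go unseen, because the events stay in the listings and in the DSMB reports.

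The conclusion assumes that no site instruction outside these documents already requires a new record for each worsening. If one exists, only the wording of the definition and the unstated numerator for the exact interval remain to be put right.

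**What to change.** 1. In SAP 3.5.1 and Protocol 9.2.2, define a TEAE as an adverse event with onset, or an increase in severity grade, after the start of the first infusion. Require a worsening to be entered as a new adverse event record dated at the worsening. For GVHD that date can come from the scheduled GVHD evaluations. With a new record, SAP 3.1.7 works unchanged.
2. In SAP 3.5.2, state that acute GVHD AESI incidence and its exact confidence interval use this definition.
3. Add a by-arm shift table of highest post-infusion MAGIC grade against last pre-infusion grade, in the form of the laboratory shift table in SAP 3.5.3. The SAP 3.1.4 baseline can serve as the reference if limited to assessments made before the infusion.

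The cost is slightly higher event counts in both arms, one extra table, and an instruction to sites on recording worsening. No new GVHD assessments are needed. That does not extend to other adverse events: no section shows that a worsening date is captured for an event kept on one record, so for those the site instruction is a real addition to data collection. An increase in severity grade is also narrower than the Protocol 8.1 trigger, which includes frequency and seriousness. It suits tables built on grade, but the choice should be stated.

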3.5.2 AEs of Special Interest

The AESIs will be reviewed by the DSMB as per the DSMB Charter. Criteria for acute and chronic GVHD and CRS can be found in Protocol Appendices E, F and G. The number and percentage of participants who had the treatment-emergent AESIs will be summarized by treatment group:

- Severity and incidence of acute GVHD
- Severity and incidence of chronic GVHD
- Severity and incidence of CRS
- Severity and incidence of infusion-related AEs
- Severity and incidence of graft failure and rejection

For GVHD, a separate table will be prepared that summarizes:

- aGVHD by MAGIC overall grade and by stage and organ involvement
- cGVHD by NIH score

Subgroup analyses may be conducted for the severity and incidence of acute GVHD by HLA Class (I, II, and I & II) and the number of HLA matches.

Incidence and severity of AESI and the corresponding exact binomial confidence intervals with 95% confidence level will be presented by treatment group.

3.5.3 Clinical Laboratory Tests

Laboratory assessments comprise safety laboratory tests (hematology, clinical chemistry) and other laboratory tests.

Descriptive statistics will be provided at each scheduled visit for selected clinical laboratory test results (hematology and clinical chemistry, appendix A) and changes from baseline.

A shift table, presenting the 2-way frequency tabulation for baseline and the worst post-baseline value according to the NCI CTCAE grade, will be provided for clinical laboratory tests

(hematology, clinical chemistry). In addition, shift tables reflecting the shift over visits will be presented for selected laboratory tests (hematology, clinical chemistry).

The number and percentage of participants with the following potentially clinically significant abnormal liver function tests will be summarized:

- Alanine aminotransferase (ALT) ≥3x upper limit of normal (ULN), ≥5xULN, ≥10xULN, and ≥20xULN
- Aspartate aminotransferase (AST) \geq 3xULN, \geq 5xULN, \geq 10xULN, and \geq 20xULN
- Total bilirubin ≥2xULN
- Potential Hy's Law cases: ALT or AST ≥3xULN, total bilirubin ≥2xULN, and alkaline phosphatase (ALP) <2xULN.

A table listing of participants with any post-baseline potentially clinically significant abnormal liver function tests will be presented.

3.5.4 Vital Signs

Descriptive statistics will be provided for vital signs by treatment group, presented as both actual values and changes from baseline over time. All vital sign data will be listed by participants.

3.5.5 Electrocardiograms

Electrocardiogram (ECG) data will be summarized by visit and treatment group for each quantitative ECG parameter using descriptive statistics. The changes from baseline to each post-baseline visit will also be summarized. All ECG parameters and details of any abnormalities will be listed by participant.

3.5.6 Physical Examinations

All Physical examination findings, including details of any abnormalities will be listed by participant.

3.6 Data Safety Monitoring Board

An independent Data and Safety Monitoring Board (DSMB) will be convened for this study to routinely monitor safety and evaluate prespecified interim analyses to stop the study early for futility. The DSMB will receive summary reports of all unexpected SAEs and AESI at least monthly. In addition, the DSMB will receive expedited reporting of all individual, unexpected, related SAEs occurring within 14 days of an infusion of study drug, and infusion related AESI of at least Grade 2 severity occurring within 24 hours of an infusion. A DSMB charter, detailing all aspects of the DSMB's scope of review and procedures as well as the frequency of DSMB meetings, will be provided in a separate document. An unblinded statistician will be assigned to the DSMB. This statistician will not be involved in any aspects of study conduct outside of the DSMB, and their role will be defined in the DSMB charter.

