1.5 Risk/Benefit

1.5.1 Potential Risks

Posoleucel primarily targets cells infected with BKV (and/or JCV), AdV, CMV, HHV-6, and/or EBV. The main risks of administration are inflammation at sites of disease and GVHD due to cross reactivity with alloantigens. Adverse events attributable to VST administration may potentially occur in a small percentage of the treated population. These can include both hematologic and non-hematologic effects, as reported in the CHARMS study.

Studies of donor-derived VSTs suggest that VSTs do not persist in patients who receive methylprednisolone at doses of ≥ 1 mg/kg/day. Therefore, if participants develop severe inflammatory reactions due to PSL a therapeutic option is to administer methylprednisolone (1 to 2 mg/kg/day). Skin rashes or skin GVHD can be treated with topical steroids.

As with other biological therapies delivered by IV infusion, possible side effects of PSL infusion include allergic reaction (anaphylaxis), decreased oxygenation, nausea/vomiting, arrhythmia, and hypertension.

Most participants (including children) are expected to have venous access catheters in place for their underlying disease and HCT procedures. Since study-related collection of blood samples and infusion of PSL or placebo will utilize these catheters, there is minimal incremental risk posed by these study-related procedures. The time points and blood volumes to be collected during this study are provided in Appendix C. Since this study will enroll both adult and pediatric participants, there are different sampling schemes (and associated volumes) based on body weight.

In order to minimize the volume of blood collected during the study, especially for pediatric participants, the blood volume of individual samples has been reduced to the maximum extent feasible, and in some cases (eg, pediatric participants weighing <20 kg) collection of blood samples at certain time points has been eliminated entirely (see Appendix C). This has been done to maintain the scientific integrity of the study while minimizing risks to participants.

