3.2 Data and Safety Monitoring Board

An independent Data and Safety Monitoring Board (DSMB) will be convened for this study to routinely monitor participant safety and evaluate prespecified interim analyses to determine whether to stop the study early for futility or success. The DSMB will receive summary reports of all serious adverse events (SAEs) and adverse events of special interest (AESI; see Section 8.1.4) at least monthly. In addition, the DSMB will receive expedited reporting of all individual,

unexpected, related SAEs occurring within 14 days of an infusion of study drug, and infusion-related AESI of at least Grade 2 severity occurring within 24 hours of an infusion. A DSMB charter, detailing all aspects of the DSMB's composition, scope of review, and procedures will be described in a separate document. In addition, the DSMB will review safety data at the following times: 1) after 9 to 15 participants have been randomized and then again at routine intervals; 2) after five children ≥1 and <6 years of age have been randomized; and 3) at additional ad hoc meeting(s) if determined necessary by the Sponsor or DSMB Chair. The DSMB will review the pre-specified interim analysis to determine whether to stop the study early for futility or success (described in Section 9.2.3). An unblinded statistician will be assigned to the DSMB. This statistician will not be involved in any aspects of study conduct outside of the DSMB, and their role will be defined in the DSMB charter.

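### SAP 3.6 limits the SAEs in the DSMB's monthly summary to unexpected ones, whereas Protocol 3.2 promises all SAEs

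*SAP*

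**What the plan says.** Protocol 3.2 states: "The DSMB will receive summary reports of all serious adverse events (SAEs) and adverse events of special interest (AESI; see Section 8.1.4) at least monthly". No SAE is filtered out of that summary.

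The corresponding sentence in SAP 3.6 reads: "The DSMB will receive summary reports of all unexpected SAEs and AESI at least monthly".

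The next sentence in each document covers expedited reports, and there the two agree in scope. In the SAP's words, "the DSMB will receive expedited reporting of all individual, unexpected, related SAEs occurring within 14 days of an infusion of study drug", together with infusion-related AESI of at least Grade 2 within 24 hours of an infusion.

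Protocol 3.2 also has the board review safety data "after 9 to 15 participants have been randomized and then again at routine intervals", again once five children aged 1 to under 6 years have been randomized, and ad hoc. Both documents leave the details of the board's scope and procedures to a separate charter, which is not among the documents available here.

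**The concern.** In the protocol, expectedness filters only the expedited individual reports, and the monthly summary is the unfiltered stream. In the SAP both SAE streams carry the filter. An SAE that is classed as expected and is not an AESI would then reach the board through neither.

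What is at stake is a safety-oversight commitment. A monthly summary prepared to the SAP sentence would deliver less than Protocol 3.2 promises, and whoever writes or maintains the charter has two conflicting sources. The primary analysis is not touched.

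**Working it through.** The point involves no sample size, power or alpha, so there is nothing to recompute. The check is a comparison of texts.

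**Step 1: the difference between the two summaries.**
- Protocol 3.2: all SAEs, plus AESI.
- SAP 3.6: unexpected SAEs, plus AESI.
- Difference: SAEs that are not unexpected and are not AESI.

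**Step 2: which events stay in as AESI.** Protocol 8.1.4 and SAP 3.5.1 list acute and chronic GVHD, graft failure and rejection, CRS, and "Infusion-related adverse events". These remain in the monthly summary under both documents, expected or not.

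**Step 3: which named risk could fall in the gap.** Protocol 1.5.1 says: "The main risks of administration are inflammation at sites of disease and GVHD due to cross reactivity with alloantigens". GVHD is an AESI. Inflammation at disease sites is not separately listed as one, so a serious case could drop out if the reference safety information makes it expected. Whether it does is not known, because that information is in the Investigator's Brochure.

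**Step 4: what the filter word means.** Protocol 8.1.2 defines an unexpected adverse drug *reaction* by comparing its nature or severity with the reference safety information. Two things follow. A listed event of inconsistent severity is still unexpected and would stay in. For an SAE judged unrelated to study drug, the documents give no rule.

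**Step 5: the streams side by side.**

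| SAE type | Monthly, Protocol 3.2 | Monthly, SAP 3.6 | Expedited, both documents |
|---|---|---|---|
| AESI, expected or not | Yes | Yes | Only if it meets the expedited criteria |
| Not AESI, related, unexpected, within 14 days of an infusion | Yes | Yes | Yes |
| Not AESI, related, unexpected, later than 14 days | Yes | Yes | No |
| Not AESI, related, expected | Yes | No | No |
| Not AESI, judged unrelated | Yes | Undefined | No |

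The last two rows are the whole of the discrepancy.

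**Step 6: is the change explained?** The SAP (V1.0, 14 November 2023) is later than the protocol (v5.0, 23 February 2022). SAP 3.1.2 points out that its day numbering differs from the protocol's. SAP 3.6 has no such note about the monthly summary.

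**The case against.** The strongest reply is that little depends on the word. The product-specific events of most concern are AESI and stay in. The board's reviews at routine intervals are a separate channel that nothing in the SAP limits, and SAP 3.6 itself keeps routine safety monitoring as the board's task. Under Protocol 8.1.3, disputes over seriousness or causality also go to the board, with no test of expectedness. The charter, not the SAP, sets what the board receives, and the word may simply have been carried over from the expedited-report sentence that follows. All of this limits the consequence, and none of it reconciles the two sentences.

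A reader might be tempted to infer more, in ways the documents do not support:

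- *That known-risk SAEs are removed from routine safety review.* Only the monthly summary is affected, and GVHD, CRS, graft failure and rejection, and infusion-related events remain in it.
- *That AESI are also limited to unexpected ones.* The grammar of the SAP sentence allows this, but SAP 3.5.1 and 3.5.2 send AESI to the board under the charter with no such limit.
- *That deaths or infections would go unseen.* This requires them to be expected under the reference safety information, which is not available. Protocol 1.5.1 does not name either among the product's risks.
- *That an imbalance between arms would be missed.* Neither document says that the monthly summaries are unblinded or split by arm.
- *That the sponsor deliberately narrowed the feed.* Nothing shows intent either way.

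**Conclusion.** The contradiction is real and confined to the monthly summary. Followed literally, SAP 3.6 omits SAEs classed as expected that are not AESI, and leaves the treatment of SAEs judged unrelated undefined. The number of events cannot be estimated, because it depends on the reference safety information. AESI, the expedited reports and the reviews at routine intervals are not affected.

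This rests on two assumptions: that the monthly summary would be prepared to the SAP sentence, and that the charter does not already settle the matter in favour of the protocol. Neither can be checked from these documents. It is a minor inconsistency between documents, worth correcting because the correction is so cheap.

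**What to change.** Delete *unexpected* from the monthly-summary sentence in SAP 3.6 so that it matches Protocol 3.2, and make the charter say the same. The expedited-report sentence, where the word belongs, needs no change.

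If the narrowing was intended, the alternative is to amend Protocol 3.2, give the reason, and define expectedness for SAEs judged unrelated to study drug.

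The first route costs one word in the SAP, a check of the charter, and slightly longer monthly listings.
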